University of California, San Diego
Antiviral Research Center
[name]
[name]
[contact]
[contact]

[contact]

E-mail

[name]
ALERT Specialist, USC
University of Southern California
Rand Schrader Clinic – 5P21
[name]
[name]

[contact] E-mail [contact]

[name]
ALERT Specialist, USC - LA County Emergency Department
LAC/USC Medical Center
Department of Internal Medicine
Division of Infectious Diseases
[name]
[name]

[contact] [contact] E-mail [contact]

Lab Technician

[name]
Phlebotomist and Lab Manager
University of California, San Diego
Antiviral Research Center
[name]
[name]
[contact]

E-mail [contact]

LIST OF ABBREVIATIONS

AE Adverse Event

ALERT Active Linkage, Engagement, and Retention to Treatment

ART Antiretroviral Therapy

ARV Antiretroviral

CCTG California Collaborative Treatment Group

CD4 CD4 Lymphocytes
CRF Case Report Form

CT Chlamydia

DSMB Data Safety and Monitoring Board

GC Gonorrhea

HIV-1 Human Immunodeficiency Virus – 1

ITT Intention to Treat LTFU Lost to Follow Up

MSM Men who have Sex with Men
NAAT Nucleic Acid Amplification Test
PID Patient Identification Number
PLWH Persons Living With HIV/AIDS

RPR Rapid Plasmin Reagin
SAE Serious Adverse Event
SOC Standard of Care

STI Sexually Transmitted Infection

TPPA Treponema Pallidum Particle Agglutination Assay

VDRL Venereal Disease Research Laboratory

LIST OF TERMS

Lost to follow up: no visit with a prescribing HIV provider in the last 180 days

Out of care: no visit with a prescribing HIV provider in the last 180 days and not on a stable antiretroviral regimen

Retention in care: maintaining at least one visit with a prescribing HIV provider within 180 days

Newly diagnosed patient: someone who has never engaged in HIV care

Patient returning to care: a patient previously seen at least once by a prescribing HIV provider who has not seen a prescribing HIV provider in the last 180 days and is not on a stable antiretroviral regimen

Prescribing HIV provider: a licensed HIV care provider who is able to prescribe HIV medications (e.g. an HIV specialty MD, Nurse practitioner, or Physician Assistant)

SCHEMA

Design: CCTG 594 is a controlled, un-blinded, two-arm, randomized (1:1) clinical

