1.1.1 Primary hypothesis

Subjects randomized to the ALERT specialist arm will have higher levels of "retention in care," defined as maintaining at least one visit with a prescribing HIV provider within 180 days, compared to subjects in the SOC arm.

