9.2 Endpoints

Primary Outcome: The CCTG 594 primary outcome is "time to LTFU" defined as the time from baseline visit to meeting the primary endpoint (LTFU defined as: no visit with a prescribing provider for more than 180 days).

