9.6.2 Analysis of Primary Outcome

A survival analysis of "time to LTFU" will be conducted. LTFU is defined as no visit with a prescribing HIV provider in the last 180 days. Time-to-LTFU will be calculated as total days between the first visit and the date when the participant reaches the definition of LTFU.

For example, a subject has his first visit on Jan 1, 2013, and another visit on Mar 1, 2013. If the subject does not have any visits thereafter, or does not have any visits until >180 days later, the subject will be counted as reaching the primary endpoint of LTFU. In this case, the subject would be LTFU if no visit occurred before Aug 27, 2013, (which is 180 days past Mar 1st). The "time-to-LTFU" will be the time period between Jan 1, 2013 and Aug 27, 2013.

At the end of the study, patients who have not reached the primary endpoint will be censored at the time of their last quarterly data extraction.

Patients who meet the primary endpoint and are found to be incarcerated will be removed from the study and censored effective at the time of their incarceration. Those who are incarcerated but return to care upon release, prior to reaching a primary endpoint, will be allowed to remain in study. Patients who change care provider to an external health facility (such as a different clinic system or a nursing facility) will be assessed for their current engagement in care; those who have completed a clinic visit with a prescribing clinician within the 180 days will be considered engaged in

care, and will not be considered LTFU. If possible, these patients will continue to come in for annual study visits.

The null hypothesis is that the median time-to-LTFU estimated using the Kaplan-Meier method will be identical in both groups. The log-rank test will be used to test the null hypothesis against the alternate hypothesis that the median time-to-LTFU is not the same between the groups.

In addition, to assess the factors associated with time-to-LTFU, Cox regression models will be performed on two subgroups, looking at each arm separately. The model will have time to LTFU as the outcome, baseline variables such as demographic, socioeconomic, psychosocial factors, risk behavior, substance use and psychiatric illness as predictors.

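### The worked example for time to LTFU miscounts its 180-day date by one day and does not match the strict inequality stated in the same paragraph (minor, wrong as written)

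*Combined protocol and SAP*

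**What the plan says.** Section 9.6.2 sets the event time as "calculated as total days between the first visit and the date when the participant reaches the definition of LTFU". It defines LTFU as having "no visit with a prescribing HIV provider in the last 180 days", the wording also used in the LTFU entry of the List of Terms and in the Schema's primary outcome.

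Its example has a first visit on Jan 1, 2013 and a second on Mar 1, 2013. The subject is an event if he never returns or "does not have any visits until >180 days later". The next sentence turns this into a date: "LTFU if no visit occurred before Aug 27, 2013, (which is 180 days past Mar 1st"). The time to LTFU "will be the time period between Jan 1, 2013 and Aug 27, 2013".

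Elsewhere the 180-day boundary is worded in several ways:

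- Section 9.2 (Endpoints): "no visit with a prescribing provider for more than 180 days", a strict inequality.
- List of Terms, and section 1.1.1 (Primary hypothesis): retention means "maintaining at least one visit with a prescribing HIV provider within 180 days", so a visit on day 180 counts as retained.
- Section 2.2.1 (Study population): describes patients who already met the LTFU criterion as unseen for 180 days or longer, a non-strict inequality.

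Section 9.0 gives a separate SAP precedence over this section. The supplied file contains no separate SAP text that settles the boundary.

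**The concern.** The example is the only place in the supplied documents where the primary endpoint becomes a calendar date. A programmer would naturally code from it. Its date does not match its own day count, and its cut-off does not match the inequality one sentence earlier. Coding the example and coding the rule would give different event status for a patient who returns right at the boundary, and different event dates for every patient who has the event.

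The boundary also has operational consequences. Reaching LTFU starts ALERT outreach in either arm (sections 5.1.4 and 6.2.4) and prompts an endpoint visit (section 6.2.5). If the patient proves to be incarcerated, it leads to removal from the study and censoring (sections 5.1.4, 8.1.6 and 9.6.2). The day on which the criterion is met should be unambiguous.

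**Working it through.** **Inputs**, all from section 9.6.2: first visit Jan 1, 2013; last visit Mar 1, 2013; stated cut-off and event date Aug 27, 2013, described as 180 days after Mar 1.

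**Step 1: try to reproduce the stated date.** Elapsed days from Mar 1 (Mar 1 = day 0): Mar 31 = 30; Apr 30 = 60; May 31 = 91; Jun 30 = 121; Jul 31 = 152; Aug 27 = 152 + 27 = 179. The stated 180 is not reproduced; day 180 is Aug 28. A leap year changes nothing, because the interval starts after February.

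**Step 2: event time from Jan 1.** Jan 1 to Mar 1, 2013 is 31 + 28 = 59 days.

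- Aug 27: 59 + 179 = 238 days (the example)
- Aug 28: 59 + 180 = 239 days (first day with a gap ≥ 180)
- Aug 29: 59 + 181 = 240 days (first day with a gap > 180)

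**Step 3: status of a first return near the boundary.** The example, read literally, makes the subject LTFU unless a visit falls before Aug 27.

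| First return (2013) | Elapsed days since Mar 1 | Example, read literally | Rule > 180 | Rule ≥ 180 |
|---|---|---|---|---|
| Aug 26 | 178 | not LTFU | not LTFU | not LTFU |
| Aug 27 | 179 | LTFU | not LTFU | not LTFU |
| Aug 28 | 180 | LTFU | not LTFU | LTFU |
| Aug 29 | 181 | LTFU | LTFU | LTFU |

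Day 179 conflicts with both inequalities. It also conflicts with the unqualified definition in the List of Terms, since a visit 179 days ago lies inside the last 180 days. Day 180 conflicts with the strict wording (sections 9.2 and 9.6.2) and with the retention definition (List of Terms, section 1.1.1), but not with section 2.2.1.

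**Step 4: inclusive counting.** With Mar 1 as day 1, Aug 27 is day 180, so the label is recovered. A count above 180 is then first reached on Aug 28, so a return on Aug 27 is still scored as LTFU against the strict rule in the same paragraph.

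**Step 5: size.** The example's event date is 239 − 238 = 1 day early under ≥ 180 (1/239 = 0.4%), or 240 − 238 = 2 days early under > 180 (2/240 = 0.8%).

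**The case against.** The best defence has four parts.

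First, the example never describes a return on day 179 or 180. Its date sentence follows one about a subject with no later visit, or none until after 180 days, so it may only be dating the event for someone already classified. This is a fair reading, and the misclassification does depend on taking the date sentence literally. The wrong date remains on either reading.

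Second, a reader might infer that a day-180 return is plainly misclassified and that the event date is always two days early. The documents do not support that. Section 2.2.1 treats 180 days or more as meeting the LTFU criterion, and the definition shared by the List of Terms, the Schema and section 9.6.2 does not say on which side day 180 falls. Under a non-strict rule, moving the date to Aug 28 would be enough and the shift would be one day. This part stands and limits the point.

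Third, inclusive counting combined with a non-strict rule would make the example consistent. But that pairing contradicts the strict inequality in the example's own paragraph, and inclusive counting does not fit a date described as so many days past another or an event time counted as days between two dates.

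Fourth, section 9.0 defers to a SAP that may settle the matter. It may, but nothing in the supplied file does so, and the example would still need correcting.

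**Conclusion.** The example is wrong as written, and the matter is minor. On elapsed days, Aug 27, 2013 is day 179, not day 180. Read literally, the example scores a day-179 return as LTFU against every wording in the documents; day 180 depends on which inequality governs. The event date is one day early under a ≥ 180 rule and two days early under a > 180 rule.

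This rests on counting elapsed days, the natural meaning of the text. The conflict with the strict rule survives inclusive counting, narrowed to a single day.

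The effect is expected to be very small. The same rule applies to both arms, and status changes only for patients whose first return falls on day 179 or 180. The documents do not say how many such returns to expect, so an effect on power or type I error cannot be computed, and none is claimed.

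A reader might also infer from the six-month visit interval in section 5.1.4 that patients seen on schedule would be counted as LTFU. That sentence is a visit expectation and not an endpoint rule, so it is not part of this point.

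**What to change.** Choose one inequality and one event-date formula for the LTFU endpoint. Use them in the List of Terms (LTFU entry), the Schema's primary outcome, sections 2.2.1, 9.2 and 9.6.2, and any separate SAP. Then correct the example to match:

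- **Under > 180**, the wording already in sections 9.2 and 9.6.2: LTFU if there is no visit on or before Aug 28, 2013 (180 days past Mar 1); event date Aug 29, 2013 (last visit + 181 days); time to LTFU 240 days.
- **Under ≥ 180**: LTFU if there is no visit before Aug 28, 2013; event date Aug 28, 2013 (last visit + 180 days); time to LTFU 239 days. The strict wording in sections 9.2 and 9.6.2, and the retention definition in the List of Terms and section 1.1.1, would then need to be brought into line.

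The eligibility wording built on the same 180-day phrase (List of Terms, Schema study population, section 4.1.4) need not change, but the plan should state whether it uses the same boundary.

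The cost is wording edits only. Data collection, sample size and the log-rank test are unaffected.

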The ALERT specialist will be responsible for tracking the on-going engagement of patients who are randomized into the intervention arm. Patients will be expected to complete visits at a minimum of every 6 months. However, the ALERT specialist will also review chart notes to review the interval that the provider recommended a medical visit. The ALERT specialist will track that the patient makes and keeps an appointment with their primary provider at the suggested interval. If the patient misses a visit at the recommended interval, the ALERT specialist will perform outreach to schedule a return visit, and again track to see that the visit is kept. The ALERT specialist will use a tracking database in order to track patient engagement, their outreach efforts and delivery of the retention modules. The ALERT specialist will record contacts (categorically) both successful and unsuccessful. They will also utilize the baseline patient contact information as well as other key notes in this tracking database. Patients who meet the LTFU primary end point, regardless of study arm will have outreach activity initiated by the ALERT specialist. This will include following the retention tracking algorithm including evaluating whether the patient is incarcerated, providing outreach calls to the patient, and reviewing the medical record. Patients who meet the primary endpoint and are found to be incarcerated will be removed from the study and censored effective at the time of their incarceration. Those who are incarcerated but then return to care upon release, prior to reaching a primary endpoint will be allowed to remain in study. Patients who are confirmed to have changed care provider to an external health facility (such as a different clinic system or a nursing facility) will be assessed for their current engagement in care; those who have completed a clinic visit with a HIV prescribing clinician within the 180 days will be considered engaged in care, and will not be considered LTFU. The ALERT specialist will request access to the patient's new HIV prescribing provider in order to assess continued follow-up care during the course of the study. In addition, if possible, these patients will continue to come to study site for the annual study visit.

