It is expected that subjects new or returning to care will have regular primary care visits at least 3-4 times in the first year. The ALERT specialist will use the clinic medical record system to abstract data on clinic visits, ART medications, serial HIV RNA and CD4 values, routine CBC and chemistry values, HIV-related and AIDS diagnoses and other medical diagnoses. Data will be entered into the study electronic database. Abstraction will be done at least quarterly for each subject. The ALERT specialist will track the status of each subject and record retention and outreach in the study database. Using data abstracted from the primary care clinic medical records system, the ALERT specialist will record all visits with a prescribing HIV provider, which will document retention as related to the primary study endpoint. For patients in the SOC arm, contact information will be collected for use in the event that the person meets the primary endpoint. Subjects in either arm who reach criteria for the LTFU primary endpoint will be identified by the ALERT specialist. The ALERT specialist will then contact the subject to assure that the patient is not incarcerated or receiving care from an HIV provider at

another facility. Once LTFU is confirmed, the ALERT worker will try to bring the patient in for a primary endpoint visit. All patients will continue to be followed after the primary endpoint (ITT) for assessment of secondary endpoints.

Education Contacts (weeks 1-24). The ALERT specialist will complete a 5 session educational curriculum called a retention module either in person or by phone to the subjects randomized to the ALERT Intervention arm. The 5 retention modules include instruction about the navigation of HIV health systems, HIV literacy, Disclosure, Medication adherence and Continuation with Care, and Self-Efficacy [MOP CCTG 594: 5.0 The 5 Retention Modules for the ALERT specialist]. The goal will be to present the majority of the material within the first 6 months, however scheduling flexibility will be allowed up to the 12 month time-point in order to maximize opportunities for patients to receive the intervention. Subjects that complete all 5 modules will be asked about their reasons motivating them to 1) participate in the study and 2) completing the 5 modules.

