8.0 CRITERIA FOR EARLY TERMINATION

8.1 Criteria for Study Subject Discontinuation

8.1.1	Pregnancy or initiation of breastfeeding during the study.
8.1.2	Subject request to withdraw participation.
8.1.3	Primary care provider request for subject withdrawal based on the provider's belief that study participation is no longer in subject's best interest.
8.1.4	Medical provider belief that the patient has life threatening clinical condition.
8.1.5	By the discretion of the site IRB, CCTG, or investigator.
8.1.6	The patient is found to be incarcerated at the time of reaching the primary endpoint.

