9.6 Analyses

9.6.1 Statistical Analysis Plan

In general, analyses will incorporate the intent-to-treat principle, namely, all randomized participants will be included in the analysis. The primary analysis compares the ALERT Intervention to the SOC arm. For all secondary analyses of interest, no adjustments for multiple comparisons will be made, and a p-value of 0.05 will be considered statistically significant. Demographic and baseline measurement variables will be summarized via standard descriptive statistics.

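### The incarceration rule censors a patient only after LTFU is reached, so it removes events according to the later outcome, and no planned analysis shows the effect

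*Combined protocol and SAP*

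**What the plan says.** The primary outcome is time to LTFU, and section 9.6.2 defines the event without any exception for incarceration: "LTFU is defined as no visit with a prescribing HIV provider in the last 180 days". The same section then adds two rules:

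- The first concerns patients who have already reached the endpoint. Any of them "found to be incarcerated will be removed from the study and censored effective at the time of their incarceration".
- The second concerns patients who come back in time, and it leaves them at risk: "Those who are incarcerated but return to care upon release, prior to reaching a primary endpoint, will be allowed to remain in study".

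Section 5.1.4 repeats the first rule ("Patients who meet the primary endpoint and are found to be incarcerated will be removed from the study"). Section 8.1.6 makes it a reason for discontinuation: "The patient is found to be incarcerated at the time of reaching the primary endpoint".

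The check is made once the LTFU criteria are reached, in either arm (section 6.2.4): "The ALERT specialist will then contact the subject to assure that the patient is not incarcerated". The trial is unblinded, and the ALERT specialist also delivers the intervention.

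Two general statements bear on the removal. Section 9.6.1 says that "analyses will incorporate the intent-to-treat principle, namely, all randomized participants will be included in the analysis". Section 6.2.4 says: "All patients will continue to be followed after the primary endpoint (ITT) for assessment of secondary endpoints".

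The text supplied contains no sensitivity analysis for incarceration. Section 9.0 defers to a SAP for details. If that is a separate file, it should be checked for one.

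**The concern.** Take two patients incarcerated on the same day. One returns to a prescriber before 180 days have passed since the last visit. That patient keeps all event-free time and remains at risk. The other reaches 180 days while incarcerated. That patient's event is removed and follow-up is cut back to the day of incarceration. Nothing known on that day separates the two; only what happens later does. Kaplan-Meier and the log-rank test assume that censoring at a given time carries no information about what follows. This rule builds that information in.

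Three things are at stake:

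- Retention is reported higher in both arms than the plan's own event definition would give.
- Removing these patients fits poorly with analysing everyone randomized and following everyone after the endpoint. It also affects the section 9.6.4 comparison of return to care after LTFU.
- Whether an event stands depends on a finding by unblinded staff who deliver the intervention. If incarceration, return or detection differed between arms, the comparison would move, and no planned output would show it.

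**Working it through.** **1. The plan's own figure.** Inputs from section 9.4.1: 150 per arm, 70% v 85% without the endpoint, two-sided alpha 0.05.

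- HR = ln(0.70)/ln(0.85) = 2.195 (stated 2.19).
- Events = 150 × (0.30 + 0.15) = 67.5.
- Freedman power = Φ(√67.5 × (2.195 − 1)/(2.195 + 1) − 1.96) = 86.7% (stated 87%).

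The stated power is reproduced. It makes no allowance for events removed by this rule.

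**2. Events removed: ceiling.** The assumptions, none of them from the documents, are: 25% other LTFU in SOC at 48 weeks; 5% or 10% incarcerated; half of those not returning; 90% of non-returners found; every non-returner reaches LTFU by day 336.

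| | 5% incarcerated | 10% incarcerated |
|---|---|---|
| Other LTFU events | 150 × 0.95 × 0.25 = 35.6 | 150 × 0.90 × 0.25 = 33.75 |
| Incarcerated, not returning | 150 × 0.05 × 0.5 = 3.75 | 150 × 0.10 × 0.5 = 7.5 |
| Total SOC events | 39.4 | 41.25 |
| Removed (90% found) | 3.4 (8.6%) | 6.75 (16.4%) |

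**3. Effect of timing.** An event by day 336 needs a last visit by day 336 − 180 = 156, so late incarcerations cannot produce one by week 48.

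- Suppose incarceration is uniform over 336 days and the last visit was 0-90 days earlier (mean 45). The share that can produce an event is about (156 + 45)/336 = 60%. That gives 0.6 × 3.4 = 2.0 and 0.6 × 6.75 = 4.0 events.
- Simulation under these assumptions gives 1.8 of 39.0 (5%) and 3.6 of 40.7 (9%).
- With all incarcerations in days 0-150, simulation removes 3.1 and 6.3 events, about 8% and 15%.

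The range is therefore roughly 5-15% of SOC events. Follow-up beyond 48 weeks would raise the counts.

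**4. Effect on the retention estimates.** This simulation assumed a 5-10% incarceration risk, equal in both arms and independent of other LTFU, with 30-50% returning, and 70% v 85% retention apart from incarceration.

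| | Rule as written | Counted as LTFU |
|---|---|---|
| SOC retention, week 48 | about 70% | 67-69% |
| ALERT retention, week 48 | about 85% | 81-84% |
| Log-rank power | 87-88% | 83-87% |

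Power is slightly higher under the rule because these events were assumed equally common in both arms and so dilute the contrast. If instead the 67.5 planned events already include them and the HR is unchanged, removing 5%, 10% or 15% lowers Freedman power to 85.0%, 83.0% or 80.9%.

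**5. Effect on the test when the arms differ.**

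- *Detection differs, no true effect.* With 90% found in ALERT and 50% in SOC, type I error is 5.3-5.5% at 5-15% incarcerated with uniform timing, and at worst 6.8% (15%, all early). With 100% v 50% or 25% found, it is 5.1-6.1% at 5% incarcerated, 6.2-6.8% at 10% and 7.8-9.5% at 15%. Most of these rejections favour ALERT.
- *Return differs.* Suppose ALERT lowers non-return from 70% to 30% and has no other effect. Two separate simulations give rejection rates of 6.6% and 8% at 10% incarcerated when these patients count as events, and 8.0% and 14% at 15%. Under the rule the rate is about 5-6% throughout.

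**The case against.** **The rule may be deliberate.** A patient in custody has not chosen to leave care, and three sections consistently decline to call this LTFU. Returners did have a visit within 180 days, so their event-free time is real, and they can still become LTFU later. This stands as a choice of what to measure. It does not justify making censoring depend on the later outcome, or leaving the effect unreported.

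**The check is nominally the same in both arms.** It is triggered by LTFU regardless of arm (sections 5.1.4 and 6.2.4). Contact details are taken from everyone (5.1.2), and the charts of all enrolled subjects are screened every three months (6.2.4). A reader might infer that SOC patients go unwatched until LTFU, so that detection must favour ALERT. The documents do not support that. Continuous outreach is for one arm only, but chart review and the LTFU check cover both. Unequal detection is possible, not shown.

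**Censoring everyone at incarceration is not a better primary analysis.** It looks like the natural cure because it no longer looks ahead. However, it gives nearly the same curves and test results, removes more events (SOC events at 10% incarcerated with 70% not returning: 42.3 counting all, 37.2 under the rule, 35.5 censoring all), and discards the returns that would show a benefit. It also needs incarceration data that are not listed for quarterly abstraction. Seeking those data by extra SOC contact would cut against section 6.2.3, which keeps study contact low to protect the outcome.

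**Scope is unclear.** Section 8.1.6 refers to incarceration at the moment of reaching the endpoint. On that reading, a patient released earlier who never returns still counts as an event, and fewer events are removed than a broad reading of section 9.6.2 suggests.

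**Conclusion.** The point holds as one of structure. Censoring is triggered by the later outcome and back-dated, it removes events that meet the 180-day definition, and nothing planned shows how many. Under the stated assumptions about 5-15% of SOC events go by week 48. Retention is about 1-3 percentage points higher in SOC and 1-4 in ALERT than if these patients counted as LTFU. The incarceration rate, return rate, timing and detection are all assumed.

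A reader might infer that the rule biases the primary test towards ALERT, or materially inflates type I error. The documents do not support this. With incarceration, return and detection equal between arms, the test is little affected. With 90% v 50% detection, type I error stays mostly near 5-6%; figures of 8-9% need 15% incarcerated and more extreme detection gaps. The stated 87% power is not wrong. This is a worthwhile, low-cost improvement and does not invalidate the primary analysis.

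**What to change.** 1. Keep patients found incarcerated at LTFU in the intent-to-treat data set. Reconcile the removal in sections 5.1.4, 8.1.6 and 9.6.2 with sections 9.6.1 and 6.2.4.
2. Pre-specify in section 9.6.2, and in the SAP if it is separate, a sensitivity analysis of the primary log-rank and Kaplan-Meier comparison that counts these patients as LTFU events on the date they reach 180 days without a visit.
3. Report by arm the number of events that the rule removed.
4. Use one wording in the three sections to say which patients the rule covers: those incarcerated on the day LTFU is reached, or those incarcerated at any time in the gap.

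The current rule may stay as the primary analysis. The cost is some wording and one extra analysis run. Visit dates are already abstracted, and incarceration status and date are already needed to apply the rule, so no new data are required.
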